3.6 Discontinuation from the Study

Subjects MUST discontinue the study for any of the following reasons:

- Termination of the study by Bristol-Myers Squibb (BMS)
- Loss of ability to freely provide consent through imprisonment or involuntarily incarceration for treatment of either a psychiatric or physical (eg, infectious disease) illness
- Subject withdraws consent
- Participation in another clinical trial with an investigational product

The reason for discontinuation from the study must be documented in the subject's medical records and entered on the appropriate case report form (CRF) page.

3.7 Post Study Drug Study Follow up

Subjects who discontinue study drug may continue to be followed.

Subjects who withdraw consent (according to Section 3.7.1) or are lost to follow-up (according to Section 3.7.2) will not be followed in this study; all other subjects will continue to be followed for collection of follow up data as required and in line with [Section 5](#), Study Assessments and Procedures.

3.7.1 Withdrawal of Consent

Subjects who request to discontinue study drug will remain in the study and must continue to be followed for protocol specified follow-up procedures. The only exception to this is when a subject specifically withdraws consent for any further contact with him/her or persons previously authorized by subject to provide this information. Subjects should notify the investigator of the decision to withdraw consent from future follow-up **in writing**, if possible. The withdrawal of consent should be explained in detail in the medical records by the investigator, as to whether the withdrawal is from further treatment with study drug only or also from study procedures and/or post treatment study follow-up, and entered on the appropriate CRF page. In the event that vital status (whether the subject is alive or dead) is being measured, publicly available information should be used to determine vital status only as appropriately directed in accordance with local law.

3.7.2 Lost to Follow-Up

All reasonable efforts must be made to locate subjects to determine and report their ongoing status. This includes follow-up with persons authorized by the subject as noted above. Lost to follow-up is defined by the inability to reach the subject after a minimum of three documented phone calls, faxes, or emails as well as lack of response by subject to one registered mail letter.

All attempts should be documented in the subject's medical records. If it is determined that the subject has died, the site will use permissible local methods to obtain the date and cause of death.

If investigator's use of third-party representative to assist in the follow-up portion of the study has been included in the subject's informed consent, then the investigator may use a Sponsor-retained third-party representative to assist site staff with obtaining subject's contact information or other public vital status data necessary to complete the follow-up portion of the study. The site staff and representative will consult publicly available sources, such as public health registries and databases, in order to obtain updated contact information. If after all attempts, the subject remains lost to follow-up, then the last known alive date as determined by the investigator should be reported and documented in the subject's medical records.

4 STUDY DRUG

Study drug includes both Investigational [Medicinal] Product (IP/IMP) and Non-investigational [Medicinal] Product (Non-IP/Non-IMP) and can consist of the following:

Table 4-1: Study Drugs for IM101603:

Product Description / Class and Dosage Form	Potency	IP/Non-IMP	Blinded or Open Label	Packaging / Appearance	Storage Conditions (per label)
Abatacept Injection 125 mg/syringe	125 mg/mL	IP	Blinded	4 syringes per kit Clear to slightly opalescent, colorless to pale yellow solution, essentially free of particulate matter on visual inspection	Store refrigerated 2 – 8 °C Protect from light Protect from freezing
Placebo for abatacept Injection	N/A	IP	Blinded	4 syringes per kit Clear to slightly opalescent, colorless to pale yellow solution, essentially free of particulate matter on visual inspection	Store refrigerated 2 – 8 °C Protect from light Protect from freezing
Abatacept Injection 125 mg/syringe	125 mg/mL	IP	Open-Label	4 syringes per kit Clear to slightly opalescent, colorless to pale yellow solution, essentially free of particulate matter on visual inspection	Store refrigerated 2 – 8 °C Protect from light Protect from freezing

4.1 Investigational Product

An investigational product, also known as investigational medicinal product in some regions, is defined as pharmaceutical form of an active substance or placebo being tested or used as a reference in a clinical study, including products already with a marketing authorization but used or assembled (formulated or packaged) differently than the authorized form, or used for an unauthorized indication, or when used to gain further information about the authorized form.

The investigational product should be stored in a secure area according to local regulations. It is the responsibility of the investigator to ensure that investigational product is only dispensed to study subjects. The investigational product must be dispensed only from official study sites by authorized personnel according to local regulations.

In this protocol, investigational products (also described in [Table 4-1](#)) are:

- Abatacept for subcutaneous injection 125mg/mL in 1 mL pre-filled syringe
- Placebo for abatacept for subcutaneous injection in 1 mL pre-filled syringe

4.2 Non-investigational Product

Other medications used as support or escape medication for preventative, diagnostic, or therapeutic reasons, as components of the standard of care for a given diagnosis, may be considered as non-investigational products.

In this protocol, non-investigational product(s) include, but are not limited to:

- Hydroxychloroquine
- Prednisone or other oral corticosteroids
- NSAIDs and analgesics
- Pilocarpine, cevimeline, cyclosporine eye drops (Restasis®), lifitegrast
- Ocular and oral lubricants
- Topical lubricants (skin emollients)

The Sponsor will not be providing these medications since they are part of subject's standard of care.

4.3 Storage of Study Drug

The product storage manager should ensure that the study drug is stored in accordance with the environmental conditions (temperature, light, and humidity) as determined by BMS. If concerns regarding the quality or appearance of the study drug arise, the study drug should not be dispensed and contact BMS immediately.

Study drug not supplied by BMS will be stored in accordance with the package insert.

Please refer to [Section 9.2.2](#) for guidance on IP records and documentation.

4.4 Method of Assigning Subject Identification

At the time of enrollment, immediately after written informed consent is obtained and before any study-related procedures are performed, each subject will be assigned a unique, sequential five-digit number beginning with 00001, 00002, 00003, and so on, for identification throughout the study. This subject number must not be reused for any other subject. The study physician or research coordinator must contact the Central Randomization System to enroll each subject into a centralized database at the time consent is obtained.

After completion of all screening evaluations and concomitant adjustment or stabilization, all eligible subjects will be randomized into the Double-Blind Treatment Phase of the study. Randomization schedules will be generated and kept by the Randomization Group within Drug Supply Management of Bristol-Myers Squibb. Randomization treatment will be assigned using a Central Randomization System in the order in which subjects qualify for treatment, not in the order of study enrollment. Subjects will be randomized on a 1:1 basis to either the abatacept treatment arm or the placebo treatment arm.

Specific instructions for randomization into the Central Randomization System will be provided in a separate manual.

4.5 Selection and Timing of Dose for Each Subject

On Office Visit days, study medication should be administered AFTER all assessments have been completed, including blood draws.

For subjects participating in the PK sub-study, the sample collection for PK on Day 15 should occur prior to dose administration.

4.5.1 Abatacept Treatment

Abatacept or matching placebo administration:

Abatacept (125 mg) or matching placebo will be administered subcutaneously (SC) once per week. On Day 1, subjects and/or personal caregivers will be trained in self-administration of SC injections using pre-filled syringes. The subject should be able to self-administer the SC injection between office visits or have an office-trained caregiver do so. All subsequent injections will be self-administered or administered by a personal caregiver. Medical staff can act as a caregiver only when the subject cannot self-administer and does not have access to a personal caregiver.

Training should be performed by investigational site personnel that are considered qualified trainers by the Investigator. Subjects or their caregivers will be trained using instructions that will be provided by BMS.

Injections sites may include the upper arms (outside area), thigh, or abdomen. When possible, injection sites and/or sides of the body should be rotated every week. The upper arm injection site should be used only by caregivers and not for self-administration.

To ensure compliance and to monitor technique “office visit” SC injections should be administered in the presence of a qualified investigational staff.

On Day 169, all subjects continuing on in the Open-label treatment period will receive abatacept, 125 mg SC, weekly.

4.5.2 Dose Modifications

4.5.2.1 Dose Modifications in the Absence of Adverse Events

Every effort should be made to give all study medications within ± 3 days of the target date during the treatment periods. The last dose before each office visit should be administered at least 4 days before the scheduled visit date. If study medication is not received within the dosing window, this dose should be skipped and the next dose must then be administered on the next scheduled target administration day.

4.5.2.2 Dose Modifications Due to Adverse Events

If abnormal laboratory test results or clinical adverse events indicate toxicity that, in the judgment of the investigator, could place the subject at risk, study drug administration should be interrupted and the investigator should notify the BMS medical monitor. Subjects may receive further study medication treatment only if full resolution of the adverse event or abnormal laboratory finding is documented.

If a dose is skipped, the next SC injection should be administered on the subsequent targeted administration day.

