3.4.2.2 Infectious Complications

Subjects who develop significant infectious complications during the study should be treated appropriately and have study medication withheld, and restarted only when clinically resolved and the investigator considers it appropriate.

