3.5 Discontinuation of Study Therapy

Subjects who discontinue treatment with investigational product during the Double-Blind Treatment Period must continue to be assessed for all efficacy measures and for safety at all remaining double-blind study visits through Week 24 (Day 169) (see [Table 5.1-2](#)). Those subjects who discontinue treatment with the study drug during the double-blind period will also require visits to assess safety and immunogenicity at 28 and 84 days after the last dose of study drug. If these visits fall within ± 14 days of a scheduled double-blind study visit, only an additional laboratory assessment (immunogenicity) needs to be performed at the scheduled study visit. Otherwise, the follow-up visits need to be performed.

Subjects who discontinue study drug during the Open-Label Treatment period should comply with protocol specified follow-up procedures as outlined in [Section 5](#). The only exception to this requirement is when a subject withdraws consent for all study procedures including post-treatment study follow-up or loses the ability to consent freely (ie, is imprisoned or involuntarily incarcerated for the treatment of either a psychiatric or physical illness).

Subjects MUST discontinue investigational product (and non-investigational product at the discretion of the investigator) for any of the following reasons:

- Subject's request to stop study treatment
- Any clinical adverse event (AE), laboratory abnormality or intercurrent illness which, in the opinion of the investigator, indicates that continuation of study therapy is not in the best interest of the subject
- Pregnancy
- Missed Doses:
 - During the double-blind period, any subject who misses greater than four consecutive doses or greater than eight total doses must be discontinued from study therapy
 - During the open-label period, any subject who misses greater than six consecutive doses or greater than ten total doses must be withdrawn from the study
- Significant non-compliance with protocol (ie, procedures, assessments, medication, etc). The investigator should discuss such issues with the BMS Medical Monitor.
- Use of prohibited medication. The investigator should discuss the use of a prohibited medication with the Medical Monitor prior to withdrawing a subject from study therapy

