5.1.3 Study Drug Administration Window

Self-administration must be observed for compliance and technique at office visits.

Administration Windows

SC injections of study medication may be administered ± 3 days around the target day. Subjects who miss the dose window should skip the SC injection and wait until the next targeted administration day.

If abnormal laboratory test results or clinical assessment indicate an adverse event that, in the judgment of the investigator, could place the subjects at risk with continued administration of study medication, study medication administration should be skipped. Subjects may receive further study medication only if resolution of the AE or abnormal laboratory finding is documented or, at a minimum, the subject's status returns to what it was at baseline.

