6 ADVERSE EVENTS

An *Adverse Event (AE)* is defined as any new untoward medical occurrence or worsening of a preexisting medical condition in a clinical investigation subject administered study drug and that does not necessarily have a causal relationship with this treatment. An AE can therefore be any unfavorable and unintended sign (such as an abnormal laboratory finding), symptom, or disease temporally associated with the use of study drug, whether or not considered related to the study drug.

The causal relationship to study drug is determined by a physician and should be used to assess all adverse events (AE). The causal relationship can be one of the following:

Related: There is a reasonable causal relationship between study drug administration and the AE.

Not related: There is not a reasonable causal relationship between study drug administration and the AE.

The term “reasonable causal relationship” means there is evidence to suggest a causal relationship.

Adverse events can be spontaneously reported or elicited during open-ended questioning, examination, or evaluation of a subject. (In order to prevent reporting bias, subjects should not be questioned regarding the specific occurrence of one or more AEs.)

Sponsor or designee will be reporting adverse events to regulatory authorities and ethics committees according to local applicable laws including European Directive 2001/20/EC and FDA Code of Federal Regulations 21 CFR Parts 312 and 320.

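### Protocol Sections 4.5.2.2 and 5.1.3 set conflicting conditions for restarting study drug when an adverse event or laboratory finding returns to an already abnormal baseline

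*Protocol*

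**What the plan says.** Two general passages of the protocol deal with holding and restarting study drug for safety.

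- **Section 4.5.2.2.** If abnormal laboratory results or clinical events indicate toxicity that the investigator thinks "could place the subject at risk, study drug administration should be interrupted and the investigator should notify the BMS medical monitor". The restart condition is: "Subjects may receive further study medication treatment only if full resolution of the adverse event or abnormal laboratory finding is documented".
- **Section 5.1.3.** If laboratory results or clinical assessment indicate an event that the investigator thinks "could place the subjects at risk with continued administration of study medication, study medication administration should be skipped". The sole condition it gives for resuming is: "if resolution of the AE or abnormal laboratory finding is documented or, at a minimum, the subject's status returns to what it was at baseline".

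Four other places bear on the point.

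- Section 3.4.2.2 covers significant infections only: drug is withheld and "restarted only when clinically resolved and the investigator considers it appropriate".
- Section 3.4.2.3 leaves continuation after a hypersensitivity reaction to the investigator's medical judgment.
- Section 4.7 refers to Section 4.5.2 for permitted dose modifications.
- Section 3.5 sets the double-blind limit: "any subject who misses greater than four consecutive doses or greater than eight total doses must be discontinued from study therapy".

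**The concern.** Both general sections are triggered by the investigator's judgment that a laboratory or clinical finding puts the subject at risk. They then set different conditions for the next dose. Section 4.5.2.2 has one route back, full resolution. Section 5.1.3 has two, and it presents return to baseline as a separate, lower minimum. They also differ on whether the medical monitor is told.

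This is a subject-safety rule. A site working from one section may re-dose a subject whom a site working from the other would keep off drug. There is a secondary effect on the data, because the length of a hold determines how many weekly doses are missed. That count feeds the discontinuation limit, and through it the set of measurements that enter the primary analysis.

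**Working it through.** The plan states no figure to reproduce here, so the check is a comparison of texts followed by simple date arithmetic.

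**Where the two conditions differ**

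| State of the finding when restart is considered | Section 4.5.2.2 | Section 5.1.3 |
|---|---|---|
| Fully resolved | permits | permits |
| Improved, but still worse than baseline | does not permit | does not permit |
| Back to a normal baseline | permits | permits |
| Back to an abnormal baseline, not fully resolved | does not permit, read literally | permits |

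Only the last row diverges.

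**Can such subjects be in the trial?** Yes. Under Section 3.3.2, criterion 3g, a subject with ALT or AST above 3 times the upper limit of normal may enter if the investigator attributes it to the disease and sees no risk. Blood counts exclude only below set floors, for example platelets below 50,000/mm³ or white cells below 2,500/mm³, so values that are low but above the floor are admissible.

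**Does anything settle precedence?** Section 4.7 points to Section 4.5.2, but it does not say that this overrides Section 5.1.3, and Section 5.1.3 is not limited to a different kind of event. The available SAP text does not address restart.

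**Effect on the data (double-blind period)**

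- More than four consecutive missed doses means five. With weekly dosing the fifth missed dose falls 5 × 7 = 35 days after the last dose taken, or 35 + 3 = 38 days when its ±3-day window closes.
- SAP Section 7.1.3 uses efficacy measurements up to 42 days after the last double-blind dose. If treatment stops at the limit, that cut-off comes 42 − 35 = 7 days after the fifth missed target day.
- The Day 169 measurement is kept if the last dose was on or after Day 169 − 42 = 127. With the ±3-day visit window this shifts to between 166 − 42 = 124 and 172 − 42 = 130.
- So a subject who stops after a last dose well before about Day 127 keeps the earlier visits in the model but contributes no Day 169 value to the primary analysis. A similar subject restarted sooner, who then stays on drug, would contribute one.
- SAP Appendix 2 also counts more than four consecutive doses missed just before Day 169 as a relevant protocol deviation, which matters for any per-protocol analysis.

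**The case against.** The case against has several parts.

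- **Resolution may already mean return to baseline.** Section 6 defines an adverse event to include "any new untoward medical occurrence or worsening of a preexisting medical condition". Resolution of a worsening can be read as a return to the prior state, and Section 4.5.2.2 is triggered by toxicity, which an entry abnormality is not. This is a fair reading and it narrows the gap. It does not close it: Section 5.1.3 lists return to baseline as something other than resolution, and Section 4.5.2.2 asks for full resolution of the abnormal laboratory finding as well as of the event.
- **Both sections bind every site.** A restart at full resolution satisfies both, and a restart at an abnormal baseline breaches Section 4.5.2.2 read literally. Section 4.7 and the duty to notify the medical monitor offer some central control. This stands in part. It weakens any claim that opposite decisions are equally compliant, but a site that consults Section 5.1.3 sees an explicit permission and no warning.
- **The infection rule is not a third contradiction.** A reader might infer that Section 3.4.2.2 must carry the same condition. The documents do not support that. It is an event-specific rule, as is the one for hypersensitivity, and may be intended as such.
- **The supplied protocol may be superseded.** Its latest visible history entry is Amendment 01 of August 2016. SAP Section 2.4 lists Amendments 6 and 8, both of which include reconciling inconsistencies, and Amendment 6 clarifies the criteria for discontinuing study therapy. None of the listed items names restart conditions. This limits the point to the supplied version.

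**Conclusion.** The conflict is real in the supplied protocol and confined to one situation: a finding that returns to an already abnormal baseline without full resolution. In that situation sites may make different re-dosing decisions, and may differ on whether they notify the medical monitor. The documents give no rate for it, so its size cannot be estimated.

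Two stronger readings are tempting and not supported.

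- A reader might infer that every adverse-event interruption is affected and that sites will re-dose under different conditions. The comparison shows agreement in every other state.
- A reader might infer that a subject held under the stricter text must pass the missed-dose limit and then leaves the primary analysis. The limit is passed only if more than four consecutive or more than eight total doses are missed. Even then the subject stays in the modified ITT model, and only measurements later than 42 days after the last dose are excluded. Sections 3.1 and 3.5 require efficacy visits to continue off drug. Sensitivity analyses 3 and 4 in SAP Section 7.1.5 use those visits, though only if both of their 10% conditions are met.

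The conclusion assumes that full resolution is read literally and that no later amendment has aligned the two sections. It is worth correcting because it concerns subject safety and is cheap to fix; the effect on the efficacy data is secondary and conditional.

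**What to change.** Reconcile Sections 4.5.2.2 and 5.1.3 so that the restart condition and the medical-monitor notification agree, with explicit wording for a subject whose baseline value was already abnormal. State whether the infection wording in Section 3.4.2.2 is a deliberate exception. Which condition applies is for the sponsor's clinical team to decide; this review takes no position.

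Before changing anything, the sponsor should check whether a later amendment already resolved the difference. If not, an amendment or administrative letter is enough. It needs no new procedure or data collection, and no change to the sample size or the analysis model.
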